Synopsis

[figure not shown]
Title	Pacemaker-based long-term monitoring of sleep apnea
Medical Device	Microport TEO® SR/DR, Microport BOREA® SR/DR, Microport ALIZEA® SR/DR
Indication	Pacemaker implantation according to current ESC guidelines
Study design	prospective non-interventional cohort study
Location	multicenter
Duration of the clinical trial / schedule	Recruitment time: 10 years Planned first patient first visit (FPFV): November 2021 Planned last patient last visit (LPLV): December 2041 Treatment duration 5 - 20 years
Discriminators	
 • severe sleep apnea, defined by an average RDI $\geq 20/h$ measured by pacemaker system in the first year after study inclusion (= observation phase). • autonomic cardiac dysfunction defined by a PRD $\geq 5.75 \text{ deg}^2$ (nativ) or $\geq 3 \text{ deg}^2$ (paced) measured by 20-minute risk ECG in the first year after study inclusion (= observation phase). • physical inactivity, defined by an average of < 2 hours of daily exercise measured by pacemaker system in the first year after study inclusion (= observation phase).
Primary objective	
 • Time to first occurrence of 3P-MACE (spontaneous myocardial infarction, stroke or death), follow up for 120 months • Time to first device-detected atrial fibrillation (first episode lasting more than 6 minutes or 24 hours), follow up for 120 months • Total burden of device-detected atrial fibrillation after 1, 3, 5 years • Incidence of severe device-detected sleep apnea (RDI $\geq 20/h$) after 1, 3, 5 years • Variability of device-detected sleep apnea after 1, 3, 5 years
Secondary objectives	
 • Incidence of common ophthalmological diseases in correlation to device-detected sleep apnea and device-detected atrial fibrillation, assessed within the first year after study enrolment • Deterioration of lung function conventional lung function testing after 5 years • Progression of subclinical peripheral artery disease, assessed by sonography, after 5 years • Progression of subclinical peripheral artery disease, assessed by ABI, after 5 years

	
 QoL assessment by EQ-5D-5L questionnaires, after 5 years (compared to baseline)
Sample size	1000
Inclusion criteria / Exclusion criteria	
Inclusion criteria:
 
 Patients with an implanted Microport TEO® SR/DR, BOREA® SR/DR, ALIZEA® SR/DR pacemaker and a fully functional system Signed informed consent from the patient 
Exclusion criteria:
 
 end-stage kidney disease (eGFR < 15 ml/min/1.73 m²) or renal-replacement therapy Addiction or another disease that does not allow the patient to assess the nature and scope as well as possible consequences of the clinical trial. Indications that the patient is unlikely to comply with the protocol (e.g., unwillingness to cooperate, inability to complete follow-up examinations). Women of childbearing age Women in pregnancy or lactation period Life expectancy < 1 year
Study timeline	
Visit 1: Inclusion and obtaining written / verbal consent. Pacemaker follow-up. Start of telemedical monitoring of the pacemaker system using SMARTVIEW® technology.
 
Visit 2: Pacemaker follow-up within the first year. Performance and discussion of the examinations (20 min risk ECG, laboratory tests, TTE, questionnaires ESS & STOP Bang & EQ-5D-5L; optional spirometry, ABPM, sonography of the peripheral vessels with ABI measurement, ophthalmologic examinations).
 
Visit 3: Pacemaker follow-up after 5 to 7 years. Discussion and optimization of telemedical monitoring of the pacemaker system using SMARTVIEW® technology. Performance and discussion of examinations (20 min risk ECG, laboratory tests, TTE, questionnaires ESS & STOP Bang & EQ-5D-5L; optional spirometry, ABPM, sonography of peripheral vessels with ABI measurement, ophthalmologic examinations).
 
End of study: The end will occur at the scheduled end of study in December 2041.

Statistical methods and analysis	
Kaplan-Meier curves are generated with respect to the primary combined and secondary endpoints and analysed with Cox proportional hazards models. Univariable and multivariable regression models are used to analyse multifactorial risk stratification, as are ROC analyses.

Study timeline

√ * optional; √ § The following laboratory values must be measured: hs-TnT, NT-proBNP, ferritin, transferrin saturation, hemoglobin, GGT, sodium, potassium, creatinine, urea, eGFR, CRP, leukocytes, platelets, total cholesterol, LDL cholesterol, HDL cholesterol, triglycerides, Lp(a).

	1 Tag X	2 in the first year (= observation period)	3 after 5-7 years	End of study
Informed consent, inclusion/exclusion criteria	√			
Demographics	√	√	√	√
Medical history, AEs and SAEs	√	√	√	√
Concomitant medication, comorbidities	√	√	√	√
On-site pacemaker follow-up	√	√	√	
Start, discussion and optimization of telemedical monitoring (SMARTVIEW®).	√	√	√	
Venous blood draw		√§	√§	
TTE		√	√	
20 min risk ECG		√	√	
Questionnaires (EQ-5D-5L, ESS, STOP Bang)		√	√	
Ophthalmologic examinations		√ *	√ *	
Spirometry		√ *	√ *	
Angiological assessment (sonography, ABI)		√ *	√ *	

ACaSA

ClinicalTrials.gov: NCT05127720

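### Read as first-year eye incidence, the ophthalmological objective cannot be met: the schedule has one optional eye examination in that year and none before it, which gives prevalence

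*Protocol*

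**What the plan says.** The protocol synopsis, under Secondary objectives, lists "Incidence of common ophthalmological diseases in correlation to device-detected sleep apnea and device-detected atrial fibrillation, assessed within the first year after study enrolment". The measurements come from the visit descriptions and the study timeline table:

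- **Visit 1:** "Inclusion and obtaining written / verbal consent. Pacemaker follow-up. Start of telemedical monitoring of the pacemaker system using SMARTVIEW® technology". No eye examination is listed.
- **Visit 2:** "Pacemaker follow-up within the first year", with "optional spirometry, ABPM, sonography of the peripheral vessels with ABI measurement, ophthalmologic examinations".
- **Visit 3:** "Pacemaker follow-up after 5 to 7 years", with "optional spirometry, ABPM, sonography of peripheral vessels with ABI measurement, ophthalmologic examinations".
- **Timeline table:** the row "Ophthalmologic examinations" is blank at Visit 1 and at the end of study, and marked optional at Visits 2 and 3. The row "Concomitant medication, comorbidities" is ticked from Visit 1 onwards, as is the row for medical history.

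The exclusion criteria do not mention eye disease. The entry on statistical methods plans Kaplan-Meier curves and Cox models for the secondary endpoints as well as the primary combined endpoint, and also lists regression models and ROC analyses. Under Discriminators, severe sleep apnea is defined by the average RDI over the whole first year.

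**The concern.** Incidence needs two things: people known to be free of the disease at a starting point, and a later look at the same people. If the first-year window applies to the eye outcome, the schedule supplies only the later look. Disease found at Visit 2 may have begun last month or ten years ago, and the examination cannot tell which.

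At stake is what this secondary objective can claim. A figure labelled incidence would be read as new disease arising under observation, and its relation to apnea or AF as exposure preceding outcome. The data would support neither. The primary objectives and the sample size are not affected.

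**Working it through.** The protocol gives no rate, effect size or power for this objective, so there is no figure to reproduce. The check compares the objective with the schedule.

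**1. Examinations inside the window.** Visit 1: none. Visit 2: one, optional. Visit 3: outside the window, at 5 to 7 years. That leaves one examination in the first year, with none before it.

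**2. Other sources of a disease-free start.** Eye disease is not an exclusion. Medical history and comorbidities at Visit 1 can flag disease already diagnosed but not undiagnosed disease, and the protocol does not use them to define who is at risk. The single examination therefore gives prevalence among those who accept it.

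**3. Fit with the stated analysis.** Kaplan-Meier and Cox methods need an event time. With one examination, the only time available from it is the date of Visit 2. A curve of those dates describes when patients were booked, not when disease began.

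**4. Order of exposure and outcome.** RDI is averaged over months 0 to 12. If Visit 2 falls at month m, the share of that averaging period after the eye examination is (12 - m)/12: half at m = 6, none at m = 12. The protocol fixes only that Visit 2 is in the first year, so this share is unknown.

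**5. Contrast with the other secondary objectives.** Lung function, peripheral artery disease and quality of life are all framed as change or comparison after 5 years, which fits Visit 2 to Visit 3. The quality-of-life objective refers to a baseline, yet its questionnaire is first scheduled at Visit 2, so Visit 2 already serves as a baseline there. Only the eye objective carries a first-year window.

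**6. Illustration, on assumed values only.** Let P be prevalence at enrolment, I the yearly incidence and t the years from enrolment to Visit 2.

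New cases = (1 - P)(1 - exp(-I·t)); share pre-dating enrolment = P / (P + new cases).

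| P | I per year | t | Found with disease | New | Share pre-dating enrolment |
|---|---|---|---|---|---|
| 5% | 4% | 1 | 8.7% | 3.7% | 57% |
| 10% | 1% | 1 | 10.9% | 0.9% | 92% |
| 30% | 0.5% | 0.5 | 30.2% | 0.2% | 99% |

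The first and last rows are the extremes over P 5-30%, I 0.5-4% and t 0.5-1.

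If Visit 1 history removed a fraction k of existing cases, P in the share becomes P(1 - k) and the new cases stay the same. Four pairs (P, I) were tried at t = 1: (10%, 1%), (20%, 2%), (5%, 4%) and (30%, 0.5%). The share is 40-98% for k = 0.5 and 12-90% for k = 0.9. For example, with P = 5%, I = 4% and k = 0.9: 0.005 / (0.005 + 0.0373) = 12%.

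**The case against.** The strongest reply is grammatical. The closing phrase of the objective directly follows the two device measures and can attach to them. The discriminator for sleep apnea, defined over that same first year, supports this. The objective would then relate first-year exposure to eye disease, with Visit 2 as baseline and Visit 3 as follow-up, and the design would be sound. This stands as a possible reading. It is not the most natural one, since the neighbouring objectives end with the time at which the outcome is assessed. If it is what was meant, the sentence still needs rewording, because it does not say over what interval incidence is counted.

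Three further points stand:

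- A reader might infer that the study will report long-standing disease as new. The protocol does not support that prediction: history and comorbidities are collected at Visit 1 and could be used to set known cases aside, possibly by a rule in an analysis plan not shown here.
- A reader might infer that the Visit 3 eye data are thrown away. Nothing says so. They are scheduled, and only the first-year reading leaves them outside this objective.
- The objective speaks of correlation, not cause, and a cross-sectional correlation can be answered with Visit 2 data. What does not fit is the word incidence.

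Leaving the matter to an analysis plan does not resolve it. Measure and window are set in the protocol's objective, and no analysis can recover onset within the first year from one examination.

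**Conclusion.** The point holds on the reading that the first-year window governs the eye outcome. The stated measure cannot then be obtained from the scheduled examinations. What can be obtained is prevalence at Visit 2 in patients who accept an optional examination, and time-to-event analysis of it would reflect visit dates. Exposure recorded after the examination is a possibility that depends on when Visit 2 occurs.

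The size of the distortion cannot be derived from the document. It names no eye diseases and gives no rates, so any single multiple for how far incidence would be overstated is unsupported. The ranges above (57-99% of findings pre-dating enrolment without use of history, as low as 12% if history removed nine in ten existing cases) rest entirely on assumed values. They show that the distortion may be large and that it depends on how well Visit 1 history identifies existing disease.

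This is a defect in the wording of one secondary objective, worth correcting because the data for a sound version are already planned.

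**What to change.** Reword the objective so that:

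1. the first-year window applies to the RDI and AF exposure;
2. the Visit 2 eye result is reported as prevalence and related to RDI and AF cross-sectionally, not by Kaplan-Meier or Cox methods;
3. incidence is new disease at Visit 3 among patients examined at Visit 2 and free of that disease then. Onset is known only to lie between the two examinations, and the analysis should respect that;
4. both results are stated to apply to patients who took the optional examinations.

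**Cost:** a change of wording, with no added procedure, since both examinations are in the schedule. The drawback is that incidence is available only after Visit 3, 5 to 7 years on, and only in patients with both examinations, a subset that may be small and selected. Adding an eye examination at enrolment would permit a first-year incidence, but at the price of a new procedure.

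### Kaplan-Meier and Cox are prescribed for the secondary endpoints, but none of the listed secondary objectives is a time to event

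*Protocol*

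**What the plan says.** Two sentences in the synopsis row on statistical methods carry the analysis. The first is: "Kaplan-Meier curves are generated with respect to the primary combined and secondary endpoints and analysed with Cox proportional hazards models". The second is: "Univariable and multivariable regression models are used to analyse multifactorial risk stratification, as are ROC analyses". No other method is named.

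The synopsis lists five secondary objectives:

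- Eye disease, related to the device findings on sleep apnea and atrial fibrillation, with this timing: "assessed within the first year after study enrolment".
- Spirometry is covered by this objective: "Deterioration of lung function conventional lung function testing after 5 years".
- For the leg arteries there are two objectives. One reads "Progression of subclinical peripheral artery disease, assessed by sonography, after 5 years"; the other is the same with ABI as the measure.
- Quality of life is worded as "QoL assessment by EQ-5D-5L questionnaires, after 5 years (compared to baseline").

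The study timeline gives Visit 2 within the first year and describes Visit 3 as "Pacemaker follow-up after 5 to 7 years". In the schedule table, the row "Questionnaires (EQ-5D-5L, ESS, STOP Bang") is ticked at Visits 2 and 3 only. Spirometry, angiology and eye examinations are ticked at the same two visits and marked optional.

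**The concern.** Kaplan-Meier and Cox need, for each patient, a date on which an event happened or a date up to which it is known not to have happened. Two primary objectives (3P-MACE and first device-detected atrial fibrillation) are worded as times to a first event and supply such dates. The secondary objectives do not. One is a finding in year 1. The other four compare two examinations several years apart, so any worsening is known only to lie somewhere between them. For lung function, ABI and EQ-5D-5L there is not even an event, because no cut-off for deterioration or progression is given.

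If the methods sentence is followed as written, the natural shortcut is to define some progression and date it at Visit 3. The curve then describes when Visit 3 took place. Hazard ratios by sleep apnea, autonomic dysfunction or inactivity become sensitive to any difference in visit timing between those groups.

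**Working it through.** **1. Objectives against method.** The plan gives no figure to reproduce here, so the first step is a comparison.

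| Secondary objective | Examined at | Type of outcome | Event date observed? |
|---|---|---|---|
| Eye disease | endpoint confined to year 1 | presence or absence | no |
| Lung function | Visits 2 and 3 (optional) | continuous change | no |
| Peripheral artery disease, sonography | Visits 2 and 3 (optional) | change, measure not specified | no |
| Peripheral artery disease, ABI | Visits 2 and 3 (optional) | continuous change | no |
| EQ-5D-5L | Visits 2 and 3 | score change | no |

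**2. Interval between the two examinations.** Visit 2 falls at 0 to 1 year and Visit 3 at 5 to 7 years. The protocol does not say what the 5 to 7 years are counted from.

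- From inclusion: shortest 5 − 1 = 4 years, longest 7 − 0 = 7 years, ratio 7/4 = 1.75.
- From Visit 2: 5 to 7 years, ratio 7/5 = 1.4.

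Under a constant rate of change, the measured change is 4/5 = 0.8 to 7/5 = 1.4 times the five-year change in the first case, and 1.0 to 1.4 times in the second.

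**3. Ordinary Kaplan-Meier and Cox with progression dated at Visit 3.** Assumptions, none from the protocol apart from the visit windows and n: n = 1000 in two groups of about equal size; Visit 2 uniform over 0–1 year and Visit 3 uniform over 5–7 years from inclusion; exponential onset after Visit 2; true hazard ratio 2; no deaths; everyone examined; 150 runs.

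| 5-year risk, reference group | Kaplan-Meier just before year 5 / true | Kaplan-Meier at year 7 / true | Cox HR (true 2) |
|---|---|---|---|
| 15% | 0% / 19% | 87% / 27% | 1.83 |
| 30% | 0% / 37% | 98% / 49% | 1.68 |
| 50% | 0% / 59% | nearly 100% / 71% | 1.47 |

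Both results can be confirmed by hand.

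*Curve.* Everyone leaves the risk set at Visit 3, so the apparent hazard at time t is p/(7 − t), where p is the proportion found to have progressed. With p roughly constant, the curve is 1 − ((7 − t)/2)^p. It starts at 0 at year 5 and must reach 1 at year 7. For the 30% row at t = 6, take p as the mean of the true 0.373 at year 5 and 0.432 at year 6, about 0.40: 1 − 0.5^0.40 = 0.24, against 0.244 simulated.

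*Hazard ratio.* Because visit timing is the same in both groups, the visit hazard cancels and Cox returns the ratio of proportions progressed. With reference-group survival S, a true ratio of 2 gives (1 − S²)/(1 − S) = 1 + S. The mean interval is 6 − 0.5 = 5.5 years, so S = (1 − risk)^(5.5/5):

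- 15%: 0.85^1.1 = 0.836, ratio 1.84.
- 30%: 0.70^1.1 = 0.676, ratio 1.68.
- 50%: 0.50^1.1 = 0.467, ratio 1.47.

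**4. Effect of visit timing alone.** Now assume no true difference (common 5-year risk 30%), with one group seen at 5–6.5 years and the other at 5.5–7 years. Cox returns a hazard ratio of about 3.3. The reason is visible directly: apart from small differences in p, the ratio of apparent hazards is (7 − t)/(6.5 − t), which is 1.5 at t = 5.5 and 2 at t = 6 and grows without limit towards 6.5. Before 5.5 years the later group can have no events at all.

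**The case against.** The strongest reply is that this is synopsis shorthand. The sentence says endpoints where the list says objectives. Its reference to the combined primary endpoint does not clearly cover first atrial fibrillation, so it may never have been meant endpoint by endpoint. Regression is also named, and model type, dichotomisation, interval censoring and the handling of deaths usually belong in a statistical analysis plan, which is not shown. That stands as a reason for moderation. It does not remove the point: the regression sentence is tied to risk stratification and withdraws nothing, and a statistical analysis plan with suitable methods would have to depart from the protocol's own sentence.

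Several stronger readings are tempting and not supported:

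- *The protocol dates events at Visit 3 and censors deaths as non-informative.* It says neither. The simulation shows what the ordinary implementation would do.
- *The two examinations are 4 to 7 years apart.* That holds only if Visit 3 is counted from inclusion; otherwise the range is 5 to 7 years. The extremes also need Visit 2 at the very start or end of year 1.
- *A visit at 5 to 7 years contradicts the five-year label.* The label can be read as not before year 5. It is loose rather than wrong.
- *EQ-5D-5L has no baseline.* No questionnaire is ticked at Visit 1, but baseline is not defined as inclusion. The first year is the observation phase in which the discriminators are also measured, so Visit 2 is a plausible baseline. It only needs to be stated.
- *Sicker patients will attend at different times.* The documents give no evidence of this. The hazard ratio of 3.3 shows how sensitive the method is and predicts nothing about this cohort.

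**Conclusion.** The point holds at moderate severity. The protocol assigns a time-to-event method to secondary objectives that have no observed event times, and the schedule cannot supply them. One result needs no assumption about disease rates: progression detected and dated at Visit 3 cannot appear before year 5, so the curve follows the visit calendar. The percentages and hazard ratios (1.47 to 1.83 for a true 2) depend on uniform visit times, exponential onset, the assumed risks and complete attendance.

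A reader might infer that the study's analysis as a whole cannot give valid estimates. The documents do not support that. Time to 3P-MACE and time to first device-detected atrial fibrillation have observed dates and suit Kaplan-Meier and Cox. The defect is confined to secondary objectives of a non-interventional cohort, four of the five resting on optional examinations.

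**What to change.** Rewrite the methods row and the secondary objectives as follows.

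- **Kaplan-Meier and Cox:** restrict to 3P-MACE, first device-detected atrial fibrillation and, if wanted, onset of severe sleep apnea dated by the device.
- **Lung function, ABI, EQ-5D-5L:** analyse the change from Visit 2 to Visit 3, adjusted for the Visit 2 value and the actual time between examinations.
- **Sonographic or other binary progression:** define progression, then use an interval-censored model, or a logistic model that accounts for interval length.
- **Year-1 eye disease:** report as prevalence, with logistic regression on device-detected sleep apnea and atrial fibrillation.
- **Deaths before Visit 3:** report alongside each of these analyses, by group, since none of the models above resolves them.
- **Timing:** state that baseline is Visit 2, state whether the 5 to 7 years run from inclusion or from Visit 2, and align the five-year label with that window.

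The cost is wording only, with no extra visits or examinations. Two limits remain and should be stated: an annualised change assumes roughly linear change between two visits, and change is estimated only in survivors who attend Visit 3 and, for the optional examinations, have them at both visits.

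### Kaplan-Meier is the only survival estimator named; if it is used for device-detected AF with deaths censored, it will overstate absolute 10-year AF risk

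*Protocol*

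**What the plan says.** Two time-to-event endpoints stand under Primary objective in the protocol synopsis. One includes death: "Time to first occurrence of 3P-MACE (spontaneous myocardial infarction, stroke or death), follow up for 120 months". The other does not: "Time to first device-detected atrial fibrillation (first episode lasting more than 6 minutes or 24 hours), follow up for 120 months".

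The row on statistical methods and analysis opens with "Kaplan-Meier curves are generated", and the whole sentence reads: "Kaplan-Meier curves are generated with respect to the primary combined and secondary endpoints and analysed with Cox proportional hazards models". It adds regression models and ROC analyses for risk stratification. It mentions neither competing events nor cumulative incidence, and it gives no rule for patients who die before AF is detected.

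The groups to be compared are set by the discriminators, the first being "severe sleep apnea, defined by an average RDI" of at least 20/h in the first year. The only exclusion tied to mortality is a life expectancy below one year.

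**The concern.** A patient who dies without AF can no longer develop it. Kaplan-Meier for AF alone has no state for death, so such a patient is ordinarily censored. The estimator then treats the patient as if AF could still occur later, at the same rate as in survivors. One minus the curve therefore estimates the probability of AF in a population where nobody dies, which is higher than the proportion of patients who will actually have AF.

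Two uses of the result are at stake. The first is the 10-year AF incidence itself. The second is the absolute difference in AF risk between discriminator groups. If mortality differs between the groups, the overstatement differs too, so the gap between the curves is not the gap in actual AF risk. The protocol states risk stratification as a purpose, and absolute risk matters for that.

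**Working it through.** **Inputs from the protocol.** The AF endpoint excludes death, its horizon is 120 months (T = 10 years), and Kaplan-Meier with Cox is the only time-to-event approach named. The protocol gives no AF rate, death rate or age, and the sample size of 1000 comes without design inputs. There is thus no figure of the plan's own to reproduce.

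**Assumed inputs.** Constant hazard *a* of first AF and constant hazard *d* of death before AF, per year. Ranges: *a* from 0.03 to 0.10, *d* from 0.01 to 0.09.

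**Formulas.**
- One minus Kaplan-Meier with deaths censored: 1 − exp(−aT)
- Actual cumulative incidence, which Aalen-Johansen estimates: a/(a+d) × [1 − exp(−(a+d)T)]

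**Worked case, a = d = 0.06.** One minus Kaplan-Meier: 1 − exp(−0.6) = 45.1%. Cumulative incidence: 0.5 × [1 − exp(−1.2)] = 34.9%. Excess: 10.2 points.

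**Range at 10 years.**

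| a | d | 1 − KM | Cumulative incidence | Excess (points) |
|---|---|---|---|---|
| 0.03 | 0.01 | 25.9% | 24.7% | 1.2 |
| 0.06 | 0.01 | 45.1% | 43.1% | 2.0 |
| 0.10 | 0.01 | 63.2% | 60.6% | 2.6 |
| 0.04 | 0.03 | 33.0% | 28.8% | 4.2 |
| 0.06 | 0.03 | 45.1% | 39.6% | 5.6 |
| 0.06 | 0.06 | 45.1% | 34.9% | 10.2 |
| 0.06 | 0.08 | 45.1% | 32.3% | 12.8 |
| 0.10 | 0.09 | 63.2% | 44.8% | 18.5 |

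The excess grows with the horizon. At 1 year it is at most 0.4 points for *d* up to 0.08. At 5 years with a = 0.06 and d = 0.05 it is 2.8 points, and at 10 years with the same hazards 8.7 points.

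**Group comparison at 10 years.**
- Equal AF hazard (0.06), death hazard 0.03 versus 0.08: one minus Kaplan-Meier is 45.1% in both groups. Cumulative incidence is 39.6% versus 32.3%, so a difference of 7.3 points in absolute risk is not shown.
- AF hazard ratio 1.3 (0.078 versus 0.06), death hazard 0.10 versus 0.05: one minus Kaplan-Meier is 54.2% versus 45.1%, a difference of 9.0 points before rounding. Cumulative incidence is 0.078/0.178 × [1 − exp(−1.78)] = 36.4% versus 0.06/0.11 × [1 − exp(−1.1)] = 36.4%, a difference of 0.0 points.

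In the first example the cause-specific hazard ratio for AF is 1.0, in the second 1.3. A Cox model that censors at death targets these values in both cases. What goes wrong is the reading of absolute risk.

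**The case against.** The strongest reply is that the protocol never says this will be done. The Kaplan-Meier sentence covers the combined primary endpoint, which is 3P-MACE, and the secondary endpoints. AF is neither. No text says that deaths are censored or that one minus Kaplan-Meier will be reported as AF risk. The methods row is a synopsis entry, and handling of death for a non-fatal endpoint is commonly settled in the statistical analysis plan, which is not shown.

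Much of this stands. Applying the sentence to AF, and censoring at death, are both inferences. The first is still the likelier reading, because AF is a primary time-to-event endpoint, no other method for such endpoints is named, and the listed secondary objectives are mostly not time-to-event. On the strict reading the protocol names no method for this endpoint, and the same wording change settles it. The point concerns the suitability of a method that the protocol does name, so it does not rest on a missing analysis plan, although that plan may already resolve it.

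A second reply is that equal AF hazards with unequal mortality should give a hazard ratio of 1, and that Kaplan-Meier curves that coincide are then no error. That is right for the question whether a discriminator is associated with the rate of AF. It does not answer how many patients in each group will have AF.

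A third reply is that the size rests wholly on assumed rates. That is also right: at 1% deaths per year the excess is only 1.2 to 2.6 points.

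**Conclusion.** The point holds as a cheap improvement limited to absolute AF risk. If Kaplan-Meier is used for time to first device-detected AF and deaths are censored, 10-year AF risk is overstated. Under constant hazards the excess runs from about 1 point (AF 3%, death 1% per year) through about 10 points (6% and 6%) to 18.5 points (10% and 9%). The direction is certain whenever deaths occur before AF; the size depends on rates that the protocol does not give.

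Three stronger readings are tempting but not supported:
- A reader might infer that the planned group comparisons of AF are invalid. The cause-specific Cox hazard ratio is unaffected by this problem; only absolute risks and their differences are.
- A reader might infer that the study expects the discriminators to raise mortality, so that bias between groups is built in. The protocol lists discriminators and an endpoint that includes death, but states no such hypothesis. Differential bias is a possibility, conditional on mortality differing.
- A reader might extend the criticism to incident severe apnea and to AF burden ("Total burden of device-detected atrial fibrillation after 1, 3, 5 years"). Both are set at 1, 3 and 5 years, no text assigns Kaplan-Meier to them, and the protocol does not define how the burden total treats time alive.

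**What to change.** In the statistical methods row, and in the analysis plan if it does not already say so, name the method for each time-to-event endpoint:

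- Time to first device-detected AF: Aalen-Johansen cumulative incidence by discriminator group, with death before AF as a competing event. Patients alive and free of AF at their last monitored date are censored; deaths are not.
- Association with the discriminators: cause-specific Cox hazard ratios for AF and, alongside them, for death without AF. A Fine-Gray model may be added as a supplement for absolute risk.
- 3P-MACE: keep Kaplan-Meier and Cox, since death is part of the endpoint.

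Deaths are already needed for 3P-MACE, so no new data are required. The cost is a few sentences and a slightly longer analysis with standard software. Reported AF incidence will be lower than Kaplan-Meier would show, and comparisons with published Kaplan-Meier figures will need a note saying so.
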